## **Statistical Analysis Plan for rPMS**

### **1. Rationale and Background**

Xeljanz® (tofacitinib) is a potent, oral janus kinase inhibitor. Xeljanz® was initially approved by the Ministry of Food and Drug Safety (MFDS) on 02 April 2014 for the treatment of adult patients with moderately to severely active Rheumatoid Arthritis (RA) who have had an inadequate response or intolerance to methotrexate. On 20 September 2019, new indications for the treatment of adult patients with moderately to severely active Ulcerative Colitis (UC) and Psoriatic Arthritis (PsA).

In clinical trials conducted on patients with moderately to severely active ulcerative colitis, the Xeljanz® (tofacitinib) demonstrated its efficacy and safety in adult patients who have had an inadequate response or intolerance to the basic treatments or biological agents. Ulcerative colitis has the chronic nature of relapse and improvement, most patients experience a number of acute deterioration throughout their life, and in the course of treatment with various drugs, they become resistant to or lose response to the treatment. Currently, there are very limited treatment options available to patients with moderately to severely active ulcerative colitis in terms of efficacy, safety, convenience of administration and Quality of Life (QoL). Therefore, for patients with limited options who do not respond to current available drugs, there are still many unmet needs for effective and rapid medications with new mechanisms of action.

CCI

### **2. Study Objectives and Others**

#### **2.1. Objectives**

The objective of this study is to identify any safety and efficacy of Xeljanz® during the post-marketing period as required by the regulation of MFDS.

#### **2.2. Study Design**

This is an open-label, non-comparative, non-interventional, prospective, and multi-center study conducted in Korean health care centers by accredited physicians (i.e., investigators). The study population will be adult patients with moderately to severely active UC who have had an inadequate response or intolerance to the basic treatments or biological agents. Clinical Severity of Ulcerative Colitis is classified as mild, moderate, or severe based on the Mayo score or partial Mayo score [Table 1].

## **Statistical Analysis Plan for rPMS**

[Table 1] Mayo Score for ulcerative colitis

Variable/Score	Criteria
Stool frequency	0 Normal number of stool 1 1-2 stools more than normal 2 3-4 stools more than normal 3 $\geq$ 5 stools more than normal
Rectal bleeding	0 No blood seen 1 Streaks of blood with stool less than half the time 2 Obvious blood with stool most of the time 3 Blood alone passed
Findings of proctosigmoidoscopy	0 Normal or inactive disease 1 Mild disease(erythema, decreased vascular pattern, mild friability) 2 Moderate disease(marked erythema, absent vascular pattern, friability, erosions) 3 Severe disease(spontaneous bleeding, ulceration)
Physician's global assessment	0 Normal 1 Mild 2 Moderate 3 Severe

Xeljanz® will be administered according to the “Dosage and Administration” of the approved labeling. There is no visit or activity mandated by this study. The investigator will collect patient data and record the information on each patient's Case Report Form (CRF).

Each investigator will sequentially enroll all patients to whom Xeljanz® is prescribed for the first time according to the local product label, and who agree to participate in this study by signing the data privacy statement. Safety is the primary endpoint of this study, which will be assessed based on Adverse Events (AEs) that have occurred between the first dose of Xeljanz® to the next visit.

As a secondary endpoint, the investigator will perform the final efficacy evaluation based on the clinical impression plus the Mayo score or partial Mayo score. The Mayo score or the partial Mayo Score at week 8, 16 and 24 (also 52 for the long-term users) is assessed to see the remission, clinical response or mucosal healing. To assess the efficacy of the Xeljanz®, Mayo score is based on a total score of 12 points by evaluating and calculating the four clinical evaluation criteria: Stool frequency, Rectal bleeding, Findings of endoscopy, and Physician's global assessment [Table 1]. Partial Mayo Score is calculated by the sum of the remaining evaluations, except for the findings of endoscopy score.

## Statistical Analysis Plan for rPMS

### 2.3. Study Population

#### 2.3.1. Inclusion Criteria

To be included in the study all patients will have received at least 1 dose of Xeljanz® for the treatment of the following indication as per local labelling:

- Moderately to severely active Ulcerative Colitis (UC) who have had an inadequate response or intolerance to the basic treatments or biological agents

#### 2.3.2. Exclusion Criteria

Patients meeting any of the following criteria as per the local labeling will not be included in the study:

1. Patients with a history of hypersensitivity to any ingredients of this product.
2. Patients with serious infection (sepsis, etc.) or active infection including localized infection.
3. Patients with active tuberculosis.
4. Patients with severe hepatic function disorder.
5. Patients with an absolute neutrophil count (ANC) < 1,000 cells/mm^3.
6. Patients with a lymphocyte count < 500 cells/mm^3.
7. Patients with a hemoglobin level < 9 g/dL.
8. Pregnant or possibly pregnant women.
9. Because of lactose contained in this drug, it should not be administered to patients with hereditary problems of galactose intolerance, Lapp lactase deficiency or glucose-galactose malabsorption.

### 2.4. Sample Size Considerations

Sample size calculations are not applicable for this study. At least 600 patients will be enrolled in this study to meet MFDS requirements.

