		7.7.2. Efficacy analysis		

Amendment 2	26 Aug 2019	7.3.1.1. Adverse event	Added the 'not applicable' in the Causality assessment	Amendment recommended by the MFDS
		7.7.1. Safety analysis	Added the definition of patients entering this study for the safety analysis Described the special populations in detail	
		7.7.2 Efficacy analysis	Added the definition of the patients entering this study for the efficacy analysis Added the efficacy analysis for incompletely long-term users	
		7.7.4. Statistical consideration	Described the statistical analysis in detail	
Amendment 3	19 Sep 2019	7.3.2. Efficacy variables 7.3.3. Efficacy evaluation	Added the final efficacy variable in efficacy variables	Added the final efficacy variable by investigator
Amendment 4	15 Oct 2019	7.1. Study design	Removed the Truelove and Witt's Score	Mayo score is more frequently used in actual medical practice
		7.3.1.1. Adverse events 7.6. Data management	Changed the criteria of AE terminology from the WHO-ART to MedDRA	Changed for digitalization and standardization of AE terminology
		7.3.2. Efficacy variables 7.3.3. Efficacy evaluation	Clarified the final efficacy evaluation	To reflect the actual medical practice

Amendment 5	06 Feb 2020	4.Milestones	Add RMP report submission timeline	Amended according to the MFDS comments	
		7.7.1.Safety analysis	Add analysis and evaluation methods for safety specification according to RMP		
Amendment 6	23 Mar 2021	5. Rationale and background	Modify number of patients in the study	Change of research methods	
		7.1 Study design	Add retrospective data collection method		

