5. RATIONALE AND BACKGROUND

Xeljanz® (tofacitinib) is a potent, oral janus kinase inhibitor. Xeljanz was initially approved by the Ministry of Food and Drug Safety (MFDS) on 02 April 2014 for the treatment of adult patients with moderately to severely active rheumatoid arthritis (RA) who have had an inadequate response or intolerance to methotrexate. On 20 September 2019, new indications for the treatment of adult patients with moderately to severely active ulcerative colitis (UC) and psoriatic arthritis (PsA).

In clinical trials conducted on patients with moderately to severely active ulcerative colitis, the Xeljanz® (tofacitinib) demonstrated its efficacy and safety in adult patients who have had an inadequate response or intolerance to the basic treatments or biological agents. Ulcerative colitis has the chronic nature of relapse and improvement, most patients experience a number of acute deterioration throughout their life, and in the course of treatment with various drugs, they become resistant to or lose response to the treatment. Currently, there are very limited treatment options available to patients with moderately to severely active ulcerative colitis in terms of efficacy, safety, convenience of administration and quality of life (QoL). Therefore, for patients with limited options who do not respond to current available drugs, there are still many unmet needs for effective and rapid medications with new mechanisms of action.

CCI

Patients who are treated with Xeljanz for at least 52 weeks will be classified as long-term users. Out of all the enrolled patients, at least 18 cases (20%) of long-term users will be followed up to see the long term safety and effectiveness of Xeljanz. This non-interventional post-marketing surveillance (PMS) study is a commitment to MFDS.

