7.7. Data analysis

Analysis will be performed for the pooled data collected by each investigator during the re-examination period. Total number of centers participating, total number of cases enrolled and retrieved, and total number of cases included in the analysis will be presented in summary tables. Evaluation of data will primarily consist of summary displays (eg, descriptive statistics, tables, and graphs).

Detailed methodology for summary and statistical analyses of data collected in this study will be documented in a Statistical Analysis Plan (SAP), which will be dated, filed and maintained by Pfizer. The SAP may modify the plans outlined in the protocol; any major modifications of primary endpoint definitions or their analyses will be reflected in a protocol amendment.

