7.7.1. Safety analysis

The primary interest of this study is the incidence of AEs investigated during the re-examination period. Incidence of each AE will be presented with 95% confidence interval. Serious, related, and/or unexpected AEs will be summarized separately.

[figure not shown]
Safety analysis will be performed for all patients registered for this study who are prescribed at least 1 dose of Xeljanz according to the local label and followed up for safety data.

To identify the factors that affect safety, subgroup analysis for various factors will be performed, including the classification of AEs by body system, and comparison of incidence of AEs by sex, age, presence of concurrent diseases, presence of concomitant medications, baseline disease activity, etc.

In case the drug was administered to special populations such as elderly people over 65, or patients with renal or hepatic disorders during the study, subgroup analysis will also be performed for each of those populations. The safety and effectiveness of Xeljanz in pediatric patients have not been established.

Unexpected AEs/ADRs will be classified by medical review with reference to the local product document. Events already included in the “Precautions for use” section of the local product document will be classified as “expected”. All other events that are not included in the “Precautions for use” section of the local product document will be classified as “unexpected”. An unexpected AE includes any events that may be symptomatically and patho-physiologically related to an event listed in the labeling, but differs from the labeled event because of greater severity or specificity.

In the case of an adverse event with important potential risks and important identified risks in relation to the safety specification under the risk management plan, or if missing information patient group is recruited, actions according to the label will be taken, and the safety information is presented separately.

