## Statistical Analysis Plan for rPMS

### Amendment Log

Version	Date	Updated by	Reason
1.0	23/Aug/2021	PPD	Initial version
1.1	02/Nov/2022	PPD	Change the imputation for end date of treatment from "The date of the final evaluation of the efficacy" to "The last follow-up date"

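### The SAP's minimum of 600 patients does not fit the protocol's 18 long-term cases labelled as 20% of enrolment, which implies about 90 patients

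*SAP*

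**What the plan says.** SAP section 2.4 gives the enrolment figure with no calculation behind it. It says "Sample size calculations are not applicable for this study" and then "At least 600 patients will be enrolled in this study to meet MFDS requirements".

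Protocol section 5 defines long-term users as patients treated for at least 52 weeks; SAP section 3.4 uses the same definition. The protocol then sets a minimum for them: "Out of all the enrolled patients, at least 18 cases (20%) of long-term users will be followed up". The next sentence reads "This non-interventional post-marketing surveillance (PMS) study is a commitment to MFDS".

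No enrolment total is visible in the protocol. Section 7.5 (study size) and part of section 5 are redacted. Protocol section 7.7 says that the "total number of cases enrolled and retrieved, and total number of cases included in the analysis will be presented in summary tables". For the primary interest of the study, section 7.7.1 says "Incidence of each AE will be presented with 95% confidence interval".

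**The concern.** The protocol names the denominator of its 20%: all enrolled patients. A count and a percentage of a named denominator fix that denominator, here at about 90. The SAP puts the same denominator at 600 or more. Both sentences are current body text, so this is not a difference between superseded and current wording.

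Two things are at stake. The first is accountability. Both figures are presented as serving the regulator, and the enrolled and analysed counts will be tabulated, so readers will set them against the plan. A study with about 90 patients and 18 long-term users would satisfy protocol section 5 and fall about 510 short of SAP section 2.4. The second is expected precision. How rare an adverse event the study can be expected to detect, and how tightly it can estimate a common one, differ greatly between 90 and 600 patients.

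**Working it through.** **Inputs.** Enrolment of at least 600 (SAP 2.4). Long-term cases of at least 18, labelled 20% of all enrolled (protocol 5). The SAP gives no power or precision formula for 600, so there is no calculation to reproduce. The check is one of proportion.

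**Total implied by the protocol**
- Direct: 18/0.20 = 90.
- If 20% is a rounded percentage: 18/0.205 = 87.8 and 18/0.195 = 92.3, so whole numbers 88 to 92.
- If 18 is 20% of the total rounded up to a whole patient: totals 86 to 90.
- Widest range: 86 to 92.

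**Reverse check from the SAP**
- 0.20 × 600 = 120 long-term cases, not 18. The difference is 120 − 18 = 102.
- 18/600 = 3.0%, not 20%.
- A total above 600 makes the mismatch larger.
- Ratio of totals: 600/92 = 6.5 and 600/86 = 7.0.

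**Alternative reading.** If 20% were a share of long-term users only, there would be 18/0.20 = 90 long-term users, and 90/600 = 15% of enrolment. Neither figure appears in the visible text, and the protocol's wording names all enrolled patients as the base.

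**Expected precision of adverse event incidence.** These are exact two-sided 95% limits. With no events the upper limit is 1 − 0.025^(1/n). The 10%, 30% and 1% incidences are assumptions for illustration; the documents give none.

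| Situation | n = 600 | n = 90 (inferred) |
|---|---|---|
| No events seen: upper limit | 0.61% | 4.0% |
| 10% incidence (60/600, 9/90) | 7.7% to 12.7% | 4.7% to 18.1% |
| 30% incidence (180/600, 27/90) | 26.4% to 33.8% | 20.8% to 40.6% |
| Chance of at least one case if true incidence is 1%: 1 − 0.99^n | 99.8% | 59.5% |

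Across the implied range, the upper limit with no events runs from 3.9% (n = 92) to 4.2% (n = 86).

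**Chronology.** Protocol section 3 logs "Modify number of patients in the study" under Amendment 6 (23 Mar 2021, section 5) and again under Amendment 7 (25 Mar 2022, section 7.5). SAP version 1.0 is dated 23 Aug 2021, between the two. SAP version 1.1 is dated 02 Nov 2022, after both, and its only logged change concerns the imputed end date of treatment. This is one way a figure could have gone stale. The log gives neither the old nor the new number, so it does not prove which one did.

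**The case against.** The strongest reply is that this is a documentation mismatch with little statistical consequence. The SAP claims no sample size calculation and sets no power or precision target. Its analysis sets are defined by patient status and treatment duration, and none of the analyses in SAP 6.2 to 6.4 uses 600, 90, 18 or 20%. Reported intervals will follow the actual count. Data collection was planned to end on 19 September 2022, before SAP version 1.1, so if that held, the 600 could no longer steer recruitment. The 90 is also back-calculated, and the section that would settle it is redacted.

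Most of this is fair and limits the harm. No estimate, test or analysis population changes, and the precision figures above describe what the plan leads a reader to expect, not what the report will contain. The redaction prevents saying which figure is right, but it does not remove the conflict. If section 7.5 gives 600 or more, the 18 (20%) in protocol section 5 is wrong; if it gives about 90, SAP 2.4 is wrong. Nor does it help that both figures are minimums. The percentage ties the minimum of 18 to a base of about 90, whereas a minimum enrolment of 600 would carry a 20% minimum of 120.

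**Conclusion.** The concern holds. The two visible figures cannot both be current: at least 600 patients against an implied 86 to 92, and a long-term minimum of 18 against 120. This rests on reading the 20% as the protocol words it, as a share of all enrolled patients. It does not depend on which figure is stale, and the visible text does not show that. The point should be fixed because the stated size and the long-term minimum are tied to a regulatory commitment and will be compared with the tabulated counts. Its reach is limited to judging an enrolment or long-term shortfall and the precision the study could have been expected to deliver.

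**What to change.** Reconcile SAP section 2.4 with protocol sections 5 and 7.5. State one enrolment total in both documents. State the long-term minimum as a count together with the percentage of that total it represents.

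The cost is wording in the SAP and, if needed, in protocol section 5. With data collection planned to have ended before SAP version 1.1, the correction adds no patients or visits. The drawback is that the plan may look less favourable once corrected: the stated size may turn out smaller, or, if 600 and 20% are both confirmed, 18 long-term users would be 102 short of the resulting 120. Any such shortfall would have to be reported as one.

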## 3. Analysis Populations

### 3.1. Safety Analysis Set

Safety analysis set will be included all patients registered for this study who are prescribed at least 1 dose of Xeljanz® according to the local label and followed up for safety data.

The cases below shall be excluded from the safety analysis set in the following order:

- 1) Subjects who have been administered Xeljanz® prior to the contract date
- 2) Subjects who have not been administered Xeljanz®
- 3) Subjects who have not met the inclusion/exclusion criterion
- 4) Subjects who have not been evaluated for any safety-related endpoints

## Statistical Analysis Plan for rPMS

- 5) Subjects who have any other significant protocol violation

### 3.2. Efficacy Analysis Set

The Efficacy analysis set will be included all patients entering this study for the safety analysis whose efficacy data are available after 24 weeks of treatment, or based on the last assessment performed at the time of treatment discontinuation if the patient does not complete the 24 weeks of treatment. If the patient does not complete the 24 weeks of treatment, the cause of discontinuation will be assessed.

The cases below shall be excluded from the efficacy analysis set in the following order:

- 1) Subjects who are excluded from the safety analysis set
- 2) Subjects without general efficacy assessment by the investigator
- 3) Subjects who are evaluated general efficacy assessment as 'Not assessable' by the investigator
- 4) Subjects who are have been administrated Xeljanz® for less than 8 weeks (56 days)

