7.2.5.1. Basic information

The following will be recorded on the CRF for each patient:

- Name of institution: Enter the name of the institution.
- Department: Enter the department name of the institution.
- Name of investigator: Enter the name of the contracted physician.
- Patient number: The investigator will sequentially assign each patient a patient identification number, which will be a 4-digit number. The total number of cases that need

to be collected will be allocated to each study site by Pfizer at the time of execution of a contract with each site.

- Completion of the study: If the patient completed 24 weeks of treatment (52 weeks for the long-term users), check “yes”. Otherwise, check “no” and choose reason for the discontinuation: AE; lack of effectiveness; others.
- Date of CRF completion: Record the date of CRF completion.
- Signature of investigator: Contracted investigator must sign after identifying the CRF.
- Confirmation of data privacy statement: If the patient has signed the data privacy statement to indicate agreement for using his/her personal and medical information, check the box of “yes” on the CRF. If not, check “no” and exclude the case from the study.

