7.3.3. Effectiveness evaluation

Effectiveness assessment will be performed by the accredited investigator in the Korean health care center. The investigator will perform the final effectiveness evaluation at baseline and after 8, 16 and 24 weeks of treatment based on the clinical impression and any of the commonly used effectiveness assessment criteria such as Mayo score or Partial Mayo score, and record the assessment results in each patient's CRF. 52nd week will be added for the long-term users. If the patient does not complete the 24 or 52 weeks of treatment, relevant data should be collected based on the last assessment performed at the time of treatment discontinuation. The final evaluation of the effectiveness will be determined by the investigator into 4 categories('Improved', 'Unchanged', 'Aggravated', 'Not assessable').

- Improved (Symptoms of ulcerative colitis have improved or showed adequate maintenance effect after taking Xeljanz)
- Unchanged (Symptoms have not changed much since taking Xeljanz)
- Aggravated (Symptoms have worsened after taking Xeljanz)
- Not assessible (Reason :)

If the overall effectiveness assessment is evaluated as 'Improved', 'Unchanged' or 'Aggravated', it is analyzed to be clinically significant. If the overall effectiveness assessment is evaluated as 'Not assessible', it is analyzed as not clinically significant. Among the 4 categories, 'Improved' is considered that the drug is effective. 'Unchanged' and 'Aggravate' are considered that there is a lack of effectiveness.

The Mayo score or the Partial Mayo score, which is referred in the effectiveness evaluation, are commonly used in actual medical practice. The Mayo score or the Partial Mayo Score at 8, 16 and 24 weeks(also 52 for the long-term users) will be assessed after the administration of Xeljanz, and Mayo Score measures the number of stool frequency, rectal bleeding, findings of endoscopy, and physician's global assessment. In total, based on the total score of 12 points, 0-2 points is rated as Remission, 3-5 as Mild, 6-10 as Moderate, and 11-12 as Severe. Partial Mayo Score is calculated by the sum of the remaining evaluations, except for the findings of endoscopy score. Based on the total score of 9 points, 0-1 is rated as Remission, 2-4 as Mild, 5-6 as Moderate and 7-9 as Severe.

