7.7.2. Effectiveness analysis

Effectiveness analysis will be performed for all patients entering this study for the safety analysis whose effectiveness data are available after 24 weeks of treatment, or based on the last assessment performed at the time of treatment discontinuation if the patient does not complete the 24 weeks of treatment. If the patient does not complete the 24 weeks of treatment, the cause of discontinuation will be assessed. For the long-term users, effectiveness analysis will also be performed after the 52 week of the treatment. Cause of discontinuation will also be performed for the long term users if the patient does not complete the 52 weeks of treatment.

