### 4.2. Efficacy Endpoints

The Mayo score or the partial Mayo score at week 8, 16, 24 and also 52 for the long-term users is assessed to see the remission, clinical response or mucosal healing. Investigator will perform the final efficacy evaluation of the drug into 4 categories based on the clinical impression plus Mayo score or partial Mayo score ('Improved', 'Unchanged', 'Aggravated', 'Not assessable').

If the patient does not complete the 24 or 52 weeks of treatment, relevant data should be collected based on the last assessment performed at the time of treatment discontinuation. The final efficacy evaluation will be determined by the investigator into 4 categories.

- Improved (Symptoms of ulcerative colitis have improved or showed adequate maintenance effect after taking Xeljanz®)
- Unchanged (Symptoms have not changed much since taking Xeljanz®)
- Aggravated (Symptoms have worsened after taking Xeljanz®)
- Not assessable

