## **Statistical Analysis Plan for rPMS**

### 5.2.2. Handling of Missing and Incomplete Dates

Missing or incomplete dates will be handled by following rule:

	Missing	Imputation
Disease duration	YYYY	0 year
	MM	0 month
	YYYY/MM	No imputation
End date of treatment	'Taking Xeljanz®'	The last follow-up date

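### The efficacy set drops rated patients treated for under 56 days, although the plan says early stoppers count at their last assessment

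*SAP*

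**What the plan says.** Protocol 7.7.2 defines the effectiveness population as safety-set patients with effectiveness data after 24 weeks, "or based on the last assessment performed at the time of treatment discontinuation if the patient does not complete the 24 weeks of treatment". The opening sentence of SAP 3.2 repeats this rule. SAP 4.2 carries it into the endpoint text: for patients who do not complete 24 or 52 weeks, "relevant data should be collected based on the last assessment performed at the time of treatment discontinuation". None of these places sets a minimum time on treatment.

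SAP 3.2 then lists four exclusions, to be applied in order:

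1. patients outside the safety set;
2. "Subjects without general efficacy assessment by the investigator";
3. patients whom the investigator rated Not assessable;
4. "Subjects who are have been administrated Xeljanz® for less than 8 weeks (56 days".

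The visible text gives no reason for the fourth. Protocol 7.7 does allow changes at this level: "The SAP may modify the plans outlined in the protocol", with an amendment required only for major changes to the primary endpoint or its analysis.

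**The concern.** The last-assessment rule exists so that patients who stop early are counted. Exclusion 4 takes back the earliest of them, and it does so by a post-baseline quantity, days on treatment. That quantity is plausibly related to outcome, because the CRF asks the investigator to "choose reason for the discontinuation: AE; lack of effectiveness; others". Protocol 7.3.3 counts ratings of Unchanged and Aggravated as lack of effectiveness, so a patient who stops in week 5 for non-response and is rated Unchanged is a recorded failure that leaves both numerator and denominator.

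What is at stake is the investigator-rated effective rate in SAP 6.3, items 5 and 6. The study has one arm, so no comparator is subject to the same selection. The baseline-to-last-value changes in item 1 may move in the same direction, though this is not quantified here. The subgroup tests and logistic regression in items 6 and 7 use the same selected set, and the direction of any effect on them cannot be determined.

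**Working it through.** **Whom exclusion 4 removes.** After exclusions 1 to 3, everyone left is rated Improved, Unchanged or Aggravated. Exclusion 4 therefore removes only ratings that SAP 4.2 would otherwise classify as effective or not effective. It does not deal with missing data.

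**The week-8 link.** 8 × 7 = 56 days, which is the first planned post-baseline assessment. SAP 6.3 accepts a week-8 score within ±15 days, that is from day 56 − 15 = 41 to day 56 + 15 = 71. Of those 31 days, 15 (days 41–55) fall below the cut. A patient scored on day 45 who continues to day 56 or beyond is kept. A patient scored on day 45 who stops on day 50 has a score inside the week-8 window and is dropped.

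**Patients still on treatment.** SAP 5.2.2 sets their end date to "The last follow-up date". A rated patient whose follow-up so far is shorter than 56 days then meets exclusion 4. The inclusion sentence of SAP 3.2 names only patients with 24-week data and patients assessed at discontinuation, so the SAP does not say whether these ongoing patients were ever in the set.

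**Size.** There is no design figure to reproduce: SAP 2.4 has no sample size calculation, and neither document gives an expected effective rate or an early stopping rate. Let

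- d = share of rated patients treated for less than 56 days,
- p = effective rate in those kept,
- e = effective rate in those excluded.

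The rate without exclusion 4 is p(1 − d) + e·d. The overstatement is p − [p(1 − d) + e·d] = d(p − e).

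All three values below are assumptions, with p = 75%:

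| d | e | d(p − e), points |
|---|---|---|
| 5% | 40% | 1.75 |
| 10% | 20% | 5.5 |
| 15% | 20% | 8.25 |
| 20% | 0% | 15.0 |
| any | 75% | 0 |
| 5% to 20% | 90% | −0.75 to −3.0 |

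As counts, with 600 rated patients, d = 10% and e = 20%: 405/540 = 75.0% among those kept, and (405 + 12)/600 = 69.5% among all rated, a difference of 5.5 points.

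Leaving e free between 0 and 1 gives bounds of d(p − 1) to d·p:

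- d = 5%: −1.25 to +3.75 points;
- d = 10%: −2.5 to +7.5 points;
- d = 20%: −5.0 to +15.0 points.

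The result does not hinge on p = 75%. With p = 80%, d = 5–20% and e = 20–40%, the overstatement runs from 0.05 × 0.40 = 2 points to 0.20 × 0.60 = 12 points.

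**Against sampling error.** The 95% half-width is 1.96 × √(0.75 × 0.25 / n), with n the number kept at d = 10%:

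- 600 rated (SAP 2.4), n = 540: 1.96 × √(0.1875/540) = 3.65 points;
- 90 rated (Protocol 5, where 18 cases are 20%, so 18/0.20 = 90), n = 81: 1.96 × √(0.1875/81) = 9.43 points.

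A 5.5-point shift exceeds the first half-width and not the second.

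**The case against.** The strongest defence is that SAP 3.2 has the usual form of an inclusion sentence narrowed by exclusions. The last-assessment rule still does work for everyone who stops between day 56 and week 24. The cut coincides with the first planned assessment, effectiveness is secondary, and Protocol 7.7 permits the SAP to differ. All of that stands, and it is why this is an unexplained narrowing and not a breach of the protocol. It does not supply a reason for the cut. Where exposure is too short to judge, the investigator can already record Not assessable, and exclusion 3 removes that patient; exclusion 4 overrides an investigator who did give a rating.

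Other points stand in part:

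- SAP 4.2 is worded as data collection, so the set itself is defined only by Protocol 7.7.2 and the opening of SAP 3.2. Those two are enough.
- The ±15-day window governs when a score is taken, not days of treatment, so only patients whose treatment or follow-up ended before day 56 are affected.
- No visits are mandated and the first planned assessment is at week 8, so d could be small. The 15-point figure needs d = 20% and e = 0 together.
- Early failures are not hidden altogether. They remain in the safety set, stopping reasons are tabulated under SAP 6.1.6, and Protocol 9.4.1 lists lack of efficacy among adverse events. None of this corrects the effective rate or shows the ratings of those dropped.
- A rationale in blacked-out protocol text cannot be ruled out. SAP 3.2, where the rule is set, shows no redaction.

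One could keep the cut, justify it and report the rate both ways. That would make the effect visible, but the main rate would still rest on a narrower set than Protocol 7.7.2 describes.

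**Conclusion.** The concern holds and should be fixed. That exclusion 4 is inconsistent with the set described in Protocol 7.7.2 and in SAP 3.2's own first sentence, and that it acts only on rated patients, follows from the text and needs no assumption.

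The direction of bias is conditional. The documents do not show that excluded patients did worse; it is plausible because of the recorded stopping reasons. The size rests wholly on assumed values: about 2 to 15 points at p = 75%, d = 5–20% and e = 0–40%. Whether that matters against sampling error depends on how many patients are rated.

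The consequence is limited to the secondary effectiveness results at up to 24 weeks. The safety set has no such exclusion, and the 52-week sets already require at least 364 days of treatment.

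**What to change.** - Delete exclusion 4 from the main efficacy set in SAP 3.2, so that rated early discontinuers enter at their last assessment as Protocol 7.7.2 states.
- State in SAP 3.2 how rated patients still on treatment with less than 56 days to last follow-up are handled.
- Keep the subset treated for at least 56 days as a labelled supplementary analysis.
- Add a table of patients treated for less than 56 days: number, treatment status or stopping reason, and investigator rating. SAP 6.1.6 covers stopping reasons overall, but not for this group or by rating.

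The cost is SAP wording and one extra table, with no new data. The reported effective rate will be lower if those now excluded did worse than those kept.
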